3.4 Analysis of secondary outcome measures

Symptoms of acute hyponatraemia (nausea, vomiting, headache, seizures) within the first 72 hours post-transplant

The number and percentage of participants experiencing each symptom will be presented by trial arm and overall. The proportion of participants experiencing each symptom at least once will be compared with exact logistic regression, because the number experiencing these symptoms may be small. The model will be adjusted for donor type (living vs deceased donor) and participant weight (<20kg vs ≥20kg pretransplant).

Statistical Analysis Plan

The degree of fluid overload experienced

This outcome is defined as proportional increase in patient weight between pretransplant weight and maximum weight in the 72 hours post-transplant. The mean proportional weight increase, with standard deviation, will be presented for each trial arm and overall. A Normal linear regression model will be used to assess whether mean proportional weight increase is different between the two treatment arms, adjusting for donor type (living vs deceased donor), participant weight pre transplant (<20kg vs ≥20kg pre-transplant) and transplant centre as a random effect. Residual plots from the normal linear regression will be examined. If there is any evidence of skew or non-constant variance, normal linear regression of log-transformed proportional weight increase will be used to assess whether mean log- proportional weight increase are different between the two treatment arms, adjusting for donor type (living vs deceased donor), participant weight pre transplant (<20kg vs ≥20kg pre-transplant) and transplant centre as a random effect.

Time to discharge from hospital

This outcome will be measured from transplant operation start time ("knife to skin") till discharge from hospital, measured in days and will be estimated using competing risks analysis. Discharge from hospital will be considered as the event and death prior to discharge will be considered as the competing risk. Median (IQR) hospital stay from the cumulative incidence curve will be reported for each trial arm and overall. Although if there are no deaths, the Kaplan-Meier method will be used. To accommodate a random centre effect and adjustment for participant weight and donor type, Cox regression analysis with a frailty term will be used to compare time to discharge between treatment arms. Participants who have not been discharged will be censored at the point of last contact. Participants who die will be censored. The estimate of the hazard of discharge from this model should be interpreted with caution because it does not properly account for the competing risk of death. However, since the number of deaths is predicted to be small, the impact of the competing risk is likely to be negligible. This will be explored by examining the cumulative incidence function for death.

Transplant kidney function at 1, 3, 7 and 90 days

This will be calculated using the creatinine-based univariate Schwartz formula (4) to determine eGFR:

eGFR = 36.5 x (height/ plasma creatinine concentration)

where height is measured in cm and plasma creatinine in micromol/L (1mg/dl = 0.01131222 micromol/L). For day 1 and 3, this data will be obtained from the blood data measurements taken routinely. If multiple measurements are recorded on the same day, then we will use the last measurement taken for each day, as this is likely to be the lowest and gives most time for creatinine to be in steady state. For day 7 and 90 a single measurement is being collected via the MACRO database and UK Transplant Registry respectively. For day 1, 3 and 7, the participant height recorded at transplant will be used. For 90 days, the participant's height at this timepoint will be used, which will be obtained from the UKTR. The mean and standard deviation of eGFR at each timepoint will be presented by trial arm and overall.

A repeated measures mixed Normal linear regression will be used to assess whether kidney function over days 1,3 and 7 are different between the two treatment arms, adjusting for donor type (living vs deceased donor), participant weight pre transplant (<20kg vs ≥20kg pre-transplant) and day of measurement. In addition, two random

Statistical Analysis Plan

effects will be included in the model to account for individual participant effects and transplant centre. Residual plots from the normal linear regression will be examined. If there is any evidence of skew or non-constant variance, repeated measures mixed normal linear regression of log-transformed eGFR will be used to assess whether mean log- eGFR are different between the two treatment arms, adjusting for donor type (living vs deceased donor), participant weight pre transplant (<20kg vs ≥20kg pre-transplant) and participant and transplant centre as random effects.

A separate mixed Normal linear regression will be used to assess whether mean eGFR is different between the two treatment arms at day 90, adjusting for donor type (living vs deceased donor), participant weight pre transplant (<20kg vs ≥20kg pre-transplant) and transplant centre as a random effect. Residual plots from the normal linear regression will be examined. If there is any evidence of skew or non-constant variance, mixed normal linear regression of log-transformed eGFR at 90 days will be used to assess whether mean log-eGFR are different between the two treatment arms, adjusting for adjusting for donor type (living vs deceased donor), participant weight pre transplant (<20kg vs ≥20kg pre-transplant) and transplant centre as a random effect.

Other electrolyte abnormalities within the first 72 hours post transplantation This includes the following:

- Hypernatraemia (defined as plasma sodium concentration > 145mmol/l)
- Hyperkalaemia (defined as plasma potassium concentration > 5.5mmol/L)
- Hypokalaemia (defined as plasma potassium concentration < 3.5mmol/L)
- Non anion-gap acidosis (defined as plasma bicarbonate < 20mmol/L and anion gap < 20mmol/L. Anion gap will be calculated as the sum of plasma sodium and plasma potassium, minus the sum of plasma chloride and plasma bicarbonate).
 Where possible, these components should be obtained simultaneously, but where this is not possible, samples should be collected within an hour.
- Hyperglycaemia (defined as random blood glucose > 5.5 mmol/L)
- Hypomagnesaemia (defined as plasma magnesium concentration < 0.7 mmol/L)
- Hyperchloraemia (defined as plasma chloride concentration > 107mmol/L)
- Excessive rate of reduction in plasma sodium concentration (defined as >1mmol/L/hour averaged over 6 hours)
- Excessive magnitude of reduction in plasma sodium concentration (defined as > 10mmol/L from pre-transplant level)

The number and percentage of participants who experience each of these events will be presented by trial arm and overall, alongside the median and interquartile range of the number of each event experienced. To test for differences in the proportion of participants experiencing each event, separate mixed logistic regression models will be used. These will be adjusted for donor type (living vs deceased donor), participant weight (<20kg vs ≥20kg pre-transplant) and transplant centre as a random effect. The adjusted odds ratio for treatment, with 95% confidence interval, will be presented from this model, with the p-value from the likelihood ratio test when including and excluding the treatment term from the model.

Maximum and minimum systolic blood pressure

The minimum and maximum systolic blood pressure will be taken for each day, for the first 3 days post-transplant (the measurement recorded in the database will have been sustained on 3 repeated values on each day). The values will be normalised to age and height percentile by the statistician, using the process as specified in https://www.nhlbi.nih.gov/files/docs/resources/heart/hbp ped.pdf and

Statistical Analysis Plan

https://www.who.int/toolkits/growth-reference-data-for-5to19-years will be used to determine the height percentiles. Heights in cm will be converted to inches by dividing by 2.54 and will utilise the height at transplant. The mean minimum and maximum normalised systolic blood pressure, with standard deviation, will be presented separately for each trial arm and overall, for each day. A repeated measures mixed Normal linear regression will be used to assess whether mean percentiles over the three days are different between the two treatment arms, adjusting for donor type (living vs deceased donor), participant weight pre transplant (<20kg vs ≥20kg pre-transplant) and day of measurement. In addition, two random effects will be included in the model to account for individual participant effects and transplant centre. Residual plots from the normal linear regression will be examined. If there is any evidence of skew or non-constant variance, repeated measures mixed normal linear regression of log-transformed percentile will be used to assess whether mean log-percentile are different between the two treatment arms, adjusting for donor type (living vs deceased donor), participant weight pre transplant (<20kg vs ≥20kg pre-transplant) and participant and transplant centre as random effects.

Number of changes in intravenous fluid composition within the first 72 hours post-transplant

A change to intravenous fluid composition will be defined as any modification to the composition of the fluid administered to the participant. The number of changes in fluid will be counted as follows:

- If the participant is initially given something different to which they were randomised, this will be counted as the first change
- Subsequent changes will be counted based on the fluid being administered before the change.
- Diluent used for drug infusions, will not be counted.

For example:

- if the participant was randomised to standard arm, was first administered Hartmann's solution, then 0.9% sodium chloride, and then Hartmann's solution again, this would be counted as two changes.
- If the participant was randomised to Plasma-Lyte, was first administered 5% glucose, then received Plasma-Lyte 148 and then Plasma-Lyte® 148 & Glucose 5%, this would count as three changes.

The mean and standard deviation of the number of changes experienced will be tabulated by treatment arm and overall, alongside the percentage of participants who had a least one change. The number of changes will be compared by treatment arm using a negative binomial model. The model will be adjusted for donor type (living vs deceased donor), participant weight pre transplant (<20kg vs ≥20kg pre-transplant) and transplant centre as a random effect. The model will also include an offset to account for the number of hours the participant was at risk of the event, up to 72 hours post transplant.

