1.5 Randomisation and Blinding Procedures

Eligible patients who have consented to participate in the PLUTO trial will be randomised via an interactive web response system, provided by Sealed Envelope. Participants will be randomised in a 1:1 ratio, to the intervention and control groups. Participants will be randomised on admission to hospital for the transplant, once the trial team are confident that the transplant will be proceeding. Before performing the randomisation, the team must re-confirm the consent/assent (it may have been several weeks since initial consent was provided). The eligibility criteria should also be re-checked prior to randomisation and the site name and patient weight must be known. Upon randomisation, the site will be provided with the allocation (Plasma-Lyte or Standard fluid therapy) and the participant's randomisation number, which will be used to identify participants throughout the trial. This number will take the form RXXXX where XXXX is a four digit participant number.

The randomisation will be stratified by transplant centre and patient weight (<20kg vs ≥20kg pre-transplant). Randomisation will further be balanced using blocks of varying, undisclosed sizes. The randomisation list will be produced by the trial statistician using SAS statistical software.

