All tests will be two-sided, p-values of less than 0.05 will be considered as evidence of a difference between treatment arms, and conditional effects will be reported. P-values will be reported to four decimal places with p-values less than 0.0001 as <0.0001. All confidence intervals presented will be 95% and two-sided. Exact confidence intervals will be used for binary data, where exact models have been used. Multiple comparisons will be performed and this may increase the probability of observing a statistically significant result by chance. No adjustments will be made to account for multiple testing. The statistical package SAS will be used to conduct analyses.

The key demographics and clinical condition of the participants will be presented for each arm of the trial to describe the cohort. In addition, a summary of transplant characteristics will be presented for each arm of the trial. A CONSORT diagram will be presented to show how participants progressed through the trial.

All analyses and accompanying tables will be presented by the treatment to which the participant was randomised. All odds, hazard and rate ratios will be presented as Plasmalyte arm versus Standard arm. A ratio which is greater than 1 indicates that the odds, hazard or rate of the event is greater in the Plasmalyte arm. 95% confidence intervals will be presented with all ratios.

P-values for regression models will be obtained by comparing models with and without the treatment term using the likelihood ratio test. In analyses where mixed models are performed, the log-likelihood will be estimated using pseudo-likelihood methods.

All analyses will be adjusted for the stratification variables (site and participant weight pre transplant: <20kg and ≥20kg) and donor type: deceased and living, as this was also felt to be an important factor which could affect the outcomes of interest. Site will be

Statistical Analysis Plan

accounted for by including a random effect and participant weight and donor type by a fixed effect in each model.

Although PLUTO is a definitive trial, the total sample size is relatively small, hence:

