- In the adjusted analyses we may observe separation of data points for outcomes with lower event rates. If this occurs, we would initially drop donor type from the model. If this does not resolve the problem, then site will be removed and a fixed effects regression model adjusting for participant weight pre transplant and donor type will be used. If this does not resolve the problem, then we would additionally drop donor type from the fixed effects regression model. If this is not suitable, then an unadjusted analysis will be performed. If the initial model is a mixed logistic regression model, then if site is removed, an exact logistic regression model will be used, where computationally possible. If exact regression is not possible, then a fixed effects logistic regression model with a Firth correction to reduce bias in the parameter estimates will be used. For each analysis, table footnotes will be used to indicate the final model type and the variables adjusted for.
- It is anticipated that in some tables and frequencies, the number presented will be less than 5. It was agreed by the TMG that all data will be presented as observed within the Data Analysis Report (as this report is only shared amongst the trial teams) but within any publications, data less than 5 will be presented as <5.

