4.4 Secondary Outcome table(s)

| Table XX Secondary outcome | me – symptoms of acute hyponatra | aemia | | |
|---|--|--------------------------|----------------|--|
| | Randomise | Randomised Treatment | | |
| | Standard care (n=) | Plasma-Lyte 148 (n=) | Total (n=) | |
| Symptoms of acute hyponatraem | nia within the first 72 hours post-tra | ansplant | , , | |
| Nausea | - | | | |
| N/Total N (%) | | | | |
| OR (95% CI) ¹ | | | | |
| p-value ² | | | | |
| Vomiting | | | | |
| N/Total N (%) | | | | |
| OR (95% CI) ¹ | | | | |
| p-value ² | | | | |
| Headache | | | | |
| N/Total N (%) | | | | |
| OR (95% CI) ¹ | | | | |
| p-value ² | | | | |
| Seizures | | | | |
| N/Total N (%) | | | | |
| OR (95% CI) ¹ | | | | |
| p-value ² | | | | |
| ¹ Adjusted for site, participant weigh | ht pre transplant and donor type. | | | |

² p-value from the likelihood ratio test when including and excluding the treatment term from the model.

³ Per participant

Adjusted for site, participant weight pre transplant and donor type.
 p-value from the likelihood ratio test when including and excluding the treatment term from the model.

Statistical Analysis Plan

| Table XX Secondary outcomes - fluids | | | |
|---|------------------------|--------------------------|----------------|
| | Randomise | ed Treatment | |
| | Standard care (n=) | Plasma-Lyte 148 (n=) | Total (n=) |
| The degree of fluid overload experienced | | | |
| Mean proportional weight increase (Standard Deviation) ¹ | | | |
| Mean difference (95% CI) ² | | | |
| p-value ³ | | | |
| | | | |
| Number of changes in intravenous fluid compos | sition within the firs | st 72 hours post-trans | plant |
| N at least one change /Total N (%) | | | |
| Mean (Standard deviation) number of changes ¹ | | | |
| Rate ratio (95% CI) ^{2,4} | | | |
| p-value ^{3,4} | | | |
| ¹ Unadjusted | | | |

⁴ Adjusted for number of hours the participant was at risk of the event

| Table XX | Secondary outcome – time to discharge | | | |
|--------------|---------------------------------------|------------------------|--------------------------|----------------|
| | | Randomised Treatment | | |
| | | Standard care (n=) | Plasma-Lyte 148 (n=) | Total (n=) |
| Time to disc | harge from hospital (days) | | | • |
| Median (I | QR) ^{1,2} | | | |
| Hazard ra | atio (95% CI) ³ | | | |
| p-value⁴ | | | | |

¹ Unadjusted

⁴ p-value from the likelihood ratio test when including and excluding the treatment term from the model.

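### The four symptom outcomes go straight to an exact model without site, against the SAP's own adjustment rule, fallback sequence and table footnotes

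*SAP*

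**What the plan says.** - **Randomisation (SAP 1.5).** "The randomisation will be stratified by transplant centre and patient weight (<20kg vs ≥20kg pre-transplant").
- **General rule (SAP 3.2).** "All analyses will be adjusted for the stratification variables (site and participant weight pre transplant: <20kg and ≥20kg) and donor type". Site is to be "accounted for by including a random effect and participant weight and donor type by a fixed effect in each model".
- **Fallback (SAP 3.2).** If separation is seen, donor type is dropped first. If that fails, site is removed and weight and donor type are kept. For a model that began as mixed logistic regression, "if site is removed, an exact logistic regression model will be used, where computationally possible"; a Firth-corrected model follows if exact regression cannot be run. Footnotes are to name the final model and its covariates.
- **Symptoms (SAP 3.4).** Each symptom is "compared with exact logistic regression, because the number experiencing these symptoms may be small". The only covariates named for this model are donor type and weight group. Site is not listed, and no exception to section 3.2 is declared.
- **Symptom table (SAP 4.4).** The odds ratio footnote reads "Adjusted for site, participant weight pre transplant and donor type". The p-value footnote specifies a likelihood ratio test of the treatment term.

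**The concern.** An analyst cannot satisfy sections 3.2, 3.4 and 4.4 together for these four outcomes. Either site is in the model or it is not, and a likelihood ratio p-value is not the p-value of an exact conditional analysis.

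The choice also sets the symptoms apart from every other secondary binary outcome. The nine other electrolyte abnormalities in section 3.4 all start from the mixed logistic model with site, including some that may be rare, such as an excessive rate of sodium reduction. The symptoms skip that step on an expectation of small counts, applied to all four with no event-count criterion. Seizures may well be rare; it does not follow that nausea and vomiting are.

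At stake are the power and interpretation of the symptom comparisons, and a model choice that could be settled after results are seen.

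**Working it through.** The contradiction is one of text; no SAP figure underlies it, so there is none to reproduce.

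**Step 1. The texts side by side**

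| Item | 3.2 general rule | 3.4 symptoms | 4.4 symptom table |
|---|---|---|---|
| Site | random effect in each model | not listed | adjusted for |
| Weight, donor type | fixed effects | adjusted for | adjusted for |
| Exact model | only after separation, and after dropping donor type has failed | from the start | not mentioned |
| p-value | likelihood ratio | not stated | likelihood ratio |

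There is also a gap. The exact-then-Firth route in 3.2 applies to a model that began as mixed logistic regression. The symptom model did not, so its fallback is unclear if exact regression cannot be computed.

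**Step 2. Size, separating the two causes**

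Inputs from the SAP: 144 participants (1.6), 1:1 allocation stratified by site (1.5), nine sites (4.1.1). Assumed, because the SAP gives none of them: site sizes of 6 to 36, the control symptom rate, an odds ratio of 0.4 within site, and the between-site SD on the log-odds scale. Stand-ins: Fisher's exact test (exact, no site), the same comparison without exactness (no site), and a Cochran-Mantel-Haenszel test stratified by site. Weight and donor type were not simulated. There were 4,000 trials per scenario, so the simulation error is about √(0.6 × 0.4 / 4000) = 0.8 points.

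Power at a 50% control rate:

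| Site SD | Exact, no site | Non-exact, no site | Site-stratified | Cost of exactness | Cost of omitting site |
|---|---|---|---|---|---|
| 0 | 71% | 76% | 76% | 5 | 0 |
| 0.8 | 60% | 67% | 71% | 7 | 4 |
| 1.2 | 50% | 58% | 66% | 8 | 8 |

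At a 10% control rate and SD 0.8, the non-exact test without site has 30.0% power and the site-stratified test 30.5%: a cost of 0.5 points.

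**Step 3. Omission of site alone, second set of assumptions**

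Nine equal sites of 16, 40% in one weight group, blocks of 2 or 4, odds ratio 0.35, 1,500 trials per scenario. Both tests are non-exact: one stratified by weight only, the other by site and weight. Power, without site against with site:

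| Base rate | SD 0 | SD 1.0 | SD 1.5 |
|---|---|---|---|
| 10% | 35.1 / 34.5% | 38.5 / 41.1% | 37.9 / 44.7% |
| 30% | 74.0 / 73.3% | 66.5 / 72.1% | 57.1 / 68.3% |
| 50% | 86.3 / 85.7% | 73.5 / 77.7% | 61.1 / 72.5% |

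Type I error without site was 4.3–5.5% at SD 0, 3.2–3.8% at SD 1.0 and 2.7–3.1% at SD 1.5. With site and weight it was 3.7–5.7% throughout. The departure is towards conservatism.

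**Step 4. Attenuation of the odds ratio**

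Take a 50% control rate and a within-site odds ratio of 0.4, and average the site-specific risks over a normal distribution of site effects. The control risk stays at 50%, so the odds ratio without site is p/(1 − p), where p is the averaged treated risk. At SD 0.8, p = 0.309 and the odds ratio is 0.309/0.691 = 0.45. At SD 1.2, p = 0.328 and it is 0.328/0.672 = 0.49. This is non-collapsibility, not confounding, since randomisation balances site.

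**The case against.** The strongest defence is that the symptom paragraph is a deliberate, specific choice with a stated reason, and specific text commonly overrides a general rule. The model it names (exact, with weight and donor type) is also one the fallback sequence can reach, at its second step, and section 3.2 provides for exact confidence intervals where exact models are used. This explains the choice but does not remove the conflict: the fallback depends on observed separation, no exception is declared, and the table still lists site.

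Four stronger readings are tempting and not supported.

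- *Omitting site costs the whole gap of about 11 points (60% against 71%).* About 7 of those points come from exactness and about 4 from site. At a 10% rate, nearer the SAP's premise of small counts, omitting site costs almost nothing at SD 0.8 or less.
- *Exact inference also pulls the odds ratio towards 1.* This has not been shown. The attenuation in Step 4 comes from omitting site; exactness was shown only to cost power.
- *The published table will misstate the adjustment.* The table is an empty shell, and section 3.2 promises footnotes naming the final model. What is wrong today is the template.
- *Symptom charting is known to differ between centres.* The SAP gives no data on this. Any effect of open-label recording would be a separate matter that site adjustment would not cure.

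It also stands that the SAP powers the trial only for the primary outcome.

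**Conclusion.** The inconsistency holds as a matter of text: the symptom analysis omits a stratification factor that section 3.2 requires in every model and that the section 4.4 footnote claims, and it bypasses the SAP's own route to an exact model. The primary analysis is untouched, and the error is conservative, so no excess of false positives is implied.

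The size depends on quantities the SAP does not give. If sites do not differ, omitting site is harmless and only the cost of exactness remains, about 5 points at a 50% rate. If symptoms are common and sites differ clearly (SD 0.8 to 1.2), omitting site costs about 4 to 8 points of power and moves a within-site odds ratio of 0.4 to about 0.45–0.49; exactness costs a further 7 to 8 points. If symptoms are rare and site variation is moderate, omitting site matters little. These figures come from simple stand-in tests, not the full models. The point merits correction before the analysis, mainly so that the model is fixed in advance.

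**What to change.** 1. In the symptoms paragraph of section 3.4, start each symptom with the mixed logistic model used for the other binary outcomes (site random effect, weight, donor type). Use the section 3.2 fallback sequence, including its Firth step, only if separation occurs.
2. Where exact inference proves necessary, for example for seizures, condition on site as a stratum if this can be computed, and report the exact p-value and interval.
3. Make the symptom table footnotes in section 4.4 state the model, the covariates and the type of p-value actually used.

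If the exact model without site is kept, the minimum is to declare it as an exception to section 3.2, name its fallback and correct both footnotes. That removes the contradiction but keeps the loss of power.

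The cost is SAP wording only: no new data, and the mixed model is already planned for other outcomes. A small downside is that, under section 3.2, the mixed model's likelihood ratio test rests on a pseudo-likelihood approximation. The model may also fail for very rare symptoms, which the fallback sequence covers. Conditioning an exact model on site does not recover the power lost to exactness.
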